#### **9.7.5.2                   Secondary Efficacy Parameter**

The key secondary efficacy parameter is the change from baseline to Week 8 in CGI-S score, which will be analyzed using the MMRM approach similar to the one used for the primary efficacy parameter.

The overall family-wise type I error rate for testing the primary and secondary efficacy parameters will be controlled at the 0.05 significance level by using the fixed sequence testing procedure. The efficacy analysis of the secondary efficacy parameter will be carried out inferentially only if the null hypothesis for the primary efficacy parameter is rejected.

#### **9.7.6 Safety Analyses**

The safety analysis will be performed for the double-blind treatment period and double-blind down-taper period separately using the Safety Population. The safety parameters will include AEs, clinical laboratory parameters, vital sign measurements, ECG parameters, C-SSRS evaluations, and the change from baseline in the age and gender-adjusted height (evaluation of growth). For each safety parameter, the last assessment made before the first dose of double-blind investigational product will be used as the baseline for all analyses of that safety parameter.

### **9.7.6.1                   *Adverse Events***

An AE (classified by preferred term) that occurs during the double-blind treatment period or during the double-blind down-taper period will be considered a treatment-emergent adverse event (TEAE) if it was not present before the date of the first dose of double-blind investigational product or was present before the date of the first dose of double-blind investigational product and increased in severity during the double-blind treatment period or during the double-blind down-taper period, respectively. If more than 1 AE is reported before the date of the first dose of double-blind investigational product and coded to the same preferred term, the AE with the greatest severity will be used as the benchmark for comparison with the AEs occurring during the double-blind treatment period or during the double-blind down-taper period that were also coded to that preferred term. An AE that occurs more than 30 days after the date of the last dose of double-blind investigational product will not be counted as a TEAE.

An AE occurring during the double-blind down-taper period will be considered a newly emergent AE if it is not present before the start of the double-blind down-taper period or was present before the start of the double-blind down-taper period but increased in severity during the double-blind down-taper period. The newly emergent AEs during the double-blind down-taper period will be summarized by body system, preferred term, and treatment group.

[figure not shown]
The number and percentage of patients reporting TEAEs in each treatment group will be tabulated by system organ class and preferred term; by system organ class, preferred term, and severity; and by system organ class, preferred term, and causal relationship to the investigational product. If more than 1 AE is coded to the same preferred term for the same patient, the patient will be counted only once for that preferred term using the most severe and most related occurrence for the summarization by severity and by causal relationship to the investigational product.

The distribution of TEAEs by severity and causal relationship to the investigational product will be summarized by treatment group.

The incidence of common ( $\geq 2\%$  of patients in any treatment group) TEAEs during the double-blind treatment period will be summarized separately by preferred term, and treatment group.

An SAE that occurred between the date of the first dose of double-blind investigational product and 30 days after the date of the last dose of double-blind investigational product in the study, inclusive, will be considered an on-therapy SAE. The incidence of SAEs and AEs leading to premature discontinuation of the study will also be summarized by study period, system organ class, preferred term, and treatment group. Listings will be presented for patients with SAEs, patients with AEs leading to premature discontinuation, and patients who died. All patients with SAEs, including those reported during the screening period or more than 30 days after the date of the last dose of the double-blind investigational product, and patients discontinuing due to AEs before the start of double-blind investigational product will be included in these listings.

Listings will be presented for patients with SAEs, patients with AEs leading to discontinuation, and patients who die (if any).

APPROVED

15 Apr 2015

A large black rectangular redaction box covers the central portion of the page. At the top, there are two smaller black rectangular redaction boxes: one on the left and one on the right, both partially overlapping the top edge of the main box. At the bottom, there are two smaller black rectangular redaction boxes: one on the left and one on the right, both partially overlapping the bottom edge of the main box.

## 9.7.6.6

## ***Investigational Product Plasma Concentration Parameters and Exposure-Response Evaluation***

Vilazodone plasma concentration data will be used to estimate population PK parameters, inter-patient, and residual variability using nonlinear mixed-effects modeling software. The study will be prospectively powered to target a 95% CI within 60% and 140% of the geometric mean estimates of clearance and volume of distribution for vilazodone, with at least 80% power. The effect of covariates on the vilazodone pharmacokinetics will also be investigated. The maximum plasma drug concentration, area under the plasma concentration versus time curve, time of maximum plasma drug concentration, half-life, apparent oral clearance and apparent volume of distribution for vilazodone will be determined and a summary (mean, median) will be reported. Vilazodone PK data will be used to support the evaluation of a potential exposure/dose-response relationship. The analysis results will be provided in a separate report.

9.7.7

Health Economics and Outcomes Research Analyses

Not applicable.

## 9.7.8 Interim Analysis

A blinded interim analysis will be conducted when approximately 75% of randomized patients have either completed the study or discontinued to obtain an estimate of the pooled standard deviation on change from baseline in the CDRS-R total score to Week 8 of the double-blind treatment period. If the estimated pooled standard deviation is larger than the assumed pooled standard deviation in the sample size calculation (see Section 9.7.9), sample sizes in placebo and vilazodone treatment groups may be increased to ensure an adequate power. However, due to the difficulties in recruiting pediatric patients with MDD, the number of patients in placebo and vilazodone treatment groups will be capped at 200.

### 9.7.9 Determination of Sample Size

The primary efficacy parameter will be the change from baseline to Week 8 of the double-blind treatment period in CDRS-R total score. [REDACTED]

## **9.8 CHANGES IN THE CONDUCT OF THE STUDY OR PLANNED ANALYSES**

Any amendment to this protocol will be provided to the Investigator in writing by FRI. No protocol amendment may be implemented (with the exceptions noted below) before it has been approved by the IRB/IEC and the signature page, signed by the Investigator, has been received by FRI. If the protocol is amended to eliminate or reduce the risk to patients, the amendment may be implemented before IRB/IEC review and approval. However, the IRB/IEC must be informed in writing of such an amendment, and approval must be obtained within reasonable time limits.

## **9.9**

## **PROTOCOL DEVIATIONS AND VIOLATIONS**

A *protocol deviation* is any change, divergence, or departure from the study design or procedures that is under the Investigator's responsibility and oversight (as defined by regulations) without prior written IRB/IEC approval or favorable opinion of an appropriate amendment and that does not have a major impact on the patient's rights, safety, or well-being, or on the integrity and authenticity of the study data. Deviations may include, but are not limited to, departure from inclusion/exclusion criteria, allowed concomitant medications, dosing or duration of treatment, failure to follow withdrawal criteria or perform the required assessments at specified time points, scheduling of visits not in accordance with specifications.

Deviating from the protocol is permitted only if absolutely necessary for the safety or clinical management of the patients and must immediately be reported to FRI. Protocol deviations should be reported to FRI (either verbally or electronically) in a timely manner from the date of discovery.

Protocol deviations that may impact patient's rights (eg, failure to obtain informed consent prior to initiating study procedures), safety, or well-being (eg, deviations that resulted in an SAE, exposure during pregnancy), or the integrity and authenticity of the study data should be reported to FRI within 24 hours, if possible.

The IRB/IEC must be notified according to the criteria and time period dictated by the IRB/IEC associated with this study.

## **9.10**

## **DATA MONITORING COMMITTEE**

An independent Data Monitoring Committee to evaluate safety study outcomes such as suicidal ideation and suicidal behavior during study conduct will be established and will operate based on a charter drafted to comply with FDA Guidance for Clinical Trial Sponsors: Establishment and Operation of Clinical Trial Data Monitoring Committees, 2006.

## **10.0 STUDY SPONSORSHIP**

This study is sponsored by Forest Research Institute, Inc.

## **10.1 STUDY TERMINATION**

FRI reserves the right to terminate the study in its entirety or at a specific study center before study completion.

## **10.2 REPORTING AND PUBLICATION**

All data generated in this study are the property of FRI. An integrated clinical and statistical report will be prepared at the completion of the study.

Publication of the results by the Investigator will be subject to mutual agreement between the Investigator and FRI and will follow FRI's Standard Operating Procedures on publications.

11.0

## **INVESTIGATOR OBLIGATIONS**

Term	Percentage
GMOs	85
Organic	92
Natural	78
Artificial	65
Organic	88
Natural	82
Artificial	70
Organic	89
Natural	84
Artificial	75
Organic	87
Natural	81
Artificial	68
Organic	86
Natural	80
Artificial	73
Organic	89
Natural	83
Artificial	76

11.2

## PERFORMANCE

### **11.5 RETENTION AND REVIEW OF RECORDS**

Records and documents pertaining to the conduct of this study, including eCRFs, source documents, consent forms, regulatory documents, clinical laboratory results, calibration logs, or reports (including, but not limited to, all local and central laboratory results and ECG reports), and medication inventory records in all formats (including, but not limited to, written, electronic, magnetic, and optical records, and scans, x-rays, and ECGs) must be retained by the Investigator for a period of at least 15 years after study completion unless local regulations or institutional policies require a longer retention period or otherwise notified in writing by FRI.

No study records shall be destroyed without notifying FRI and providing FRI the opportunity to arrange long-term storage for such study records or authorizing in writing the destruction of records after the required retention period.

The Investigator must permit access to any documentation relating to the study upon request of FRI or applicable regulatory authorities. If the Investigator for the study retires, relocates, or for other reasons withdraws from the responsibility of keeping the study records, custody must be transferred to a suitable alternate custodian employee of the institution or to a suitably qualified and responsible third party. FRI must be notified in writing of the name and address of the new custodian in advance of the transfer.

For Canadian study centers only: All records and documents pertaining to the conduct of the study must be retained for a 25-year period in accordance with the Canadian Food and Drugs Act and Regulations.

**11.6 PATIENT CONFIDENTIALITY**

All patient records will only be identified by initials and PID number. Patients' names are not to be transmitted to FRI. The Investigator will keep a master patient list on which the PID number and the full name, address, and telephone number of each patient are listed.

**APPENDIX III. CONCOMITANT MEDICATIONS**

## APPENDIX IV. BLOOD SAMPLING AND SHIPPING INSTRUCTIONS

### Pharmacokinetic Blood Collection and Processing Procedure

#### Specimen Tube Collection Preparation

[figure not shown]
- Adhere the FRI provided label to a Vacutainer® tube containing K2EDTA
- Prechill (eg, in an ice bath or refrigerator) the labeled Vacutainer tube and a polypropylene tube

[figure not shown]
#### Plasma Collection Procedure

[figure not shown]
- Collect blood into the prechilled Vacutainer tube; invert the tube gently 8-10 times to mix the blood and anticoagulant. Place the tube in an ice-water bath (use crushed ice).
- Centrifuge the tube (within 30 minutes from the time the blood is drawn) at a minimum 2500 rpm for 10 minute at approximately 4°C (ie, refrigerated centrifuge). In absence of a refrigerated centrifuge, the blood tubes should be chilled in ice for at least 10 minutes prior to centrifuging. Blood samples should still be centrifuged within 30 minutes of blood collection.
- After centrifugation, transfer harvested plasma immediately into a prechilled, labeled, polypropylene tube provided by the central laboratory. Ensure the tube has the appropriate label marked with study number, subject identification number, date, and time of collection.
- The tube will then be flash-frozen in a dry ice and alcohol bath (with isopropyl alcohol, ethanol, acetone, or methanol) and should be stored at approximately -70°C (or up to 6 weeks at -20°C).
- Enter the actual time that the blood sample was collected on the appropriate form of the eCRF.
- Send the frozen sample to the central laboratory according to the central laboratory sample shipment guide.

#### Shipping Guide from the Study Center to the Central Laboratory

[figure not shown]
Samples will be shipped from the study center to the central laboratory on the first available appropriate date after sample collection, and can be batch-shipped but no later than six weeks after sample collection if stored at a temperature approximately -20°C. The central laboratory will provide packaging, labeling, and shipping instructions to the study center. Plasma samples will be shipped on sufficient dry ice to keep them frozen for at least 96 hours.

[figure not shown]

[figure not shown]

**APPENDIX VIII. COLUMBIA-SUICIDE SEVERITY RATING SCALE -  
BASELINE**

**COLUMBIA-SUICIDE SEVERITY  
RATING SCALE  
(C-SSRS)**

Baseline  
Version 1/14/09

*Posner, K.; Brent, D.; Lucas, C.; Gould, M.; Stanley, B.; Brown, G.; Fisher, P.;  
Zelazny, J.; Burke, A.; Oquendo, M.; Mann, J.*

[figure not shown]
*Disclaimer:*

[figure not shown]
*This scale is intended for use by trained clinicians. The questions contained in the Columbia-Suicide Severity Rating Scale are suggested probes. Ultimately, the determination of the presence of suicidality depends on clinical judgment.*

[figure not shown]
*Definitions of behavioral suicidal events in this scale are based on those used in **The Columbia Suicide History Form**, developed by [name] and [name], Conte Center for the Neuroscience of Mental Disorders (CCNMD), New York State Psychiatric Institute, [name]. (Oquendo M. A., Halberstam B. & Mann J. J., Risk factors for suicidal behavior: utility and limitations of research instruments. In M.B. First [Ed.] Standardized Evaluation in Clinical Practice, pp. 103 -130, 2003.)*

*For reprints of the C-SSRS contact [name]., New York State Psychiatric Institute, [name]; inquiries and training requirements contact [contact]*

© 2008 The Research Foundation for Mental Hygiene, Inc.

**APPENDIX IX. COLUMBIA-SUICIDE SEVERITY RATING SCALE - SINCE LAST VISIT**

**COLUMBIA-SUICIDE SEVERITY  
RATING SCALE  
(C-SSRS)**  
Since Last Visit  
Version 1/14/09

*Posner, K.; Brent, D.; Lucas, C.; Gould, M.; Stanley, B.; Brown, G.; Fisher, P.; Zelazny, J.; Burke, A.; Oquendo, M.; Mann, J.*

*Disclaimer:*

[figure not shown]
*This scale is intended for use by trained clinicians. The questions contained in the Columbia-Suicide Severity Rating Scale are suggested probes. Ultimately, the determination of the presence of suicidality depends on clinical judgment.*

[figure not shown]
*Definitions of behavioral suicidal events in this scale are based on those used in **The Columbia Suicide History Form**, developed by [name] and [name], Conte Center for the Neuroscience of Mental Disorders (CCNMD), New York State Psychiatric Institute, [name]. (Oquendo M. A., Halberstam B. & Mann J. J., Risk factors for suicidal behavior: utility and limitations of research instruments. In M.B. First [Ed.] Standardized Evaluation in Clinical Practice, pp. 103 -130, 2003.)*

[figure not shown]
*For reprints of the C-SSRS contact [name]., New York State Psychiatric Institute, [name]; inquiries and training requirements contact [contact]*

© 2008 The Research Foundation for Mental Hygiene, Inc.

3.0 LIST OF ABBREVIATIONS

| | |
|-----------|--|
| AE | adverse event |
| ALP | alkaline phosphatase |
| ALT | alanine aminotransferase |
| ANCOVA | analysis of covariance |
| ANOVA | analysis of variance |
| AST | aspartate aminotransferase |
| BP | blood pressure |
| CDRS-R | Children's Depression Rating Scale-Revised |
| CGI-I | Clinical Global Impression - Improvement |
| CGI-S | Clinical Global Impression - Severity |
| CMH | Cochran-Mantel-Haenszel |
| CRF | case report form |
| C-SSRS | Columbia-Suicide Severity Rating Scale |
| DSM-IV-TR | Diagnostic and Statistical Manual of Mental Disorders, Fourth Edition, Text Revision |
| ECG | electrocardiogram, electrocardiographic |
| eCRF | electronic case report form |
| ET | early termination |
| GLMM | generalized linear mixed model |
| IP | investigational product |
| ITT | intent to treat |
| LAR | legally authorized representative |
| LOCF | last observation carried forward |
| MDD | major depressive disorder |
| MedDRA | Medical Dictionary for Regulatory Activities |

| | |
|------|---|
| MMRM | mixed-effects model for repeated measures |
| OC | observed cases |
| PCS | potentially clinically significant |
| PID | patient identification |
| PK | pharmacokinetic |
| QTc | QT interval corrected for heart rate |
| QTcB | QT interval corrected for heart rate using the Bazett formula |
| QTcF | QT interval corrected for heart rate using the Fridericia formula |
| SAE | serious adverse event |
| SAP | statistical analysis plan |
| SI | Le Système International d'Unités (International System of Units) |
| TBL | total bilirubin |
| TEAE | treatment-emergent adverse event |
| ULN | upper limit of normal laboratory reference range |

[figure not shown]
4.0 INTRODUCTION

[figure not shown]
This statistical analysis plan (SAP) provides a more technical and detailed elaboration of the statistical analyses of the efficacy and safety data as outlined and/or specified in the protocol of Study VLZ-MD-22. Specifications of tables, figures, and data listings are contained in a separate document. The statistical analysis for pharmacokinetic/pharmacodynamic parameters will be specified in a separate document.

[figure not shown]
Study VLZ-MD-22 is a multicenter, randomized, double-blind, placebo- and active-controlled, parallel-group, flexible-dose study in pediatric patients, ages 7-17 years, who have been diagnosed with major depressive disorder (MDD) using the Diagnostic and Statistical Manual of Mental Disorders, Fourth Edition, Text Revision (DSM-IV-TR) diagnostic criteria for a minimum duration of 6 weeks. This study includes 3 treatment groups: placebo, vilazodone, and fluoxetine. A total of 400 patients (160 per group for placebo and vilazodone, 80 for fluoxetine) are planned to be randomized.

[figure not shown]
The study duration will be 10 weeks, starting with a 1-week screening period, followed by an 8-week of double-blind treatment period, and a 1-week of down-taper period. Patients must provide assent to participate and their parent/guardian/ legally authorized representative (LAR), and caregiver must provide written informed consent prior to the conduct of any study-specific procedures.

5.0 **OBJECTIVES**

The objective of this study is to evaluate the efficacy, safety, and tolerability of vilazodone compared with placebo in pediatric outpatients (7-17 years of age) with MDD.

In addition, the study is designed to obtain pharmacokinetic (PK) data to define the PK profile of vilazodone in the pediatric population (7-17 years of age).

6.0 PATIENT POPULATIONS

Four populations will be considered in the statistical analysis of the study.

6.1 SCREENED POPULATION

The Screened Population will consist of all patients who underwent a Screening Visit and received a screening number, and for whom the informed consent was obtained.

6.2 RANDOMIZED POPULATION

The Randomized Population will consist of all patients in the Screened Population who were randomized to a treatment group in the study.

6.3 SAFETY POPULATION

The Safety Population will consist of all patients in the Randomized Population who received at least 1 dose of double-blind investigational product.

6.4 INTENT-TO-TREAT POPULATION

The Intent-to-Treat (ITT) Population will consist of all patients in the Safety Population who had baseline and at least 1 postbaseline assessment of the Children's Depression Rating Scale-Revised (CDRS-R) total score.

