9.2 MEASUREMENT OF TREATMENT COMPLIANCE

[REDACTED]

10.0 **EFFICACY ANALYSES**

The efficacy analyses will be based on the ITT Population. *Baseline* for efficacy is defined as the last nonmissing efficacy assessment (at or prior to Visit 2) before the first dose of double-blind investigational product. All statistical tests will be 2-sided hypothesis tests performed at the 5% level of significance for main effects. All confidence intervals will be 2-sided 95% confidence intervals, unless stated otherwise.

For efficacy analyses in which study center is a factor, a small center will be defined as a center with fewer than 2 patients in any treatment group in the ITT Population. Small centers will be pooled to form pseudo-centers so that each treatment group includes at least 2 ITT patients within the center. Pooling will be done (within each country first) using the following algorithm:

Based on the number of ITT patients, small centers will be ordered from the largest to the smallest, and centers of the same size will be ordered from the largest center code to the smallest center code. The pooling process starts with the largest small center from the top, which will be pooled with the smallest from the bottom until a non-small pseudo center is formed. The process will be repeated using the small centers left out after the first pass. If any centers are left out at the end of the process, they will be pooled with the smallest pseudo center. If there is more than 1 smallest pseudo center, the pseudo center with the smallest center code will be selected. In case that the pseudo center formed by pooling all small centers is still a small center, it will be pooled with the smallest non-small center. If there is more than 1 smallest non-small center, the one with the smallest center code will be selected.

These pseudo-centers will be used for all efficacy analyses when the model is adjusted for study center.

By-visit analyses based on the mixed-effects model for repeated measures (MMRM) using the observed case (OC) approach will be performed for all continuous efficacy parameters with multiple post-baseline measurements.

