10.1 PRIMARY EFFICACY PARAMETER

The primary efficacy parameter is the change from baseline to Week 8 in CDRS-R total score. The primary analysis for comparing vilazodone vs placebo will be performed using an MMRM with treatment group, pooled study center, visit, and treatment-group-by-visit interaction as the fixed effects and the baseline value and baseline-value-by-visit interaction as the covariates. An unstructured covariance matrix will be used to model the covariance of within-patient scores. The Kenward-Roger approximation (Kenward and Roger, 1997) will be used to estimate denominator degrees of freedom. This analysis will only use the observed cases of postbaseline scores without imputation of missing values.

To control the overall type I error rate for the multiple comparisons across the primary and the secondary hypotheses, a fixed sequence procedure will be applied. Details are provided in Section [10.2](#).

In addition, two sensitivity analyses, LOCF and pattern-mixture model approaches, will be performed on the primary efficacy parameter. The LOCF approach is based on an analysis-of-covariance (ANCOVA) model including treatment group and pooled study center as factors and baseline CDRS-R total score as a covariate. Another sensitivity analysis using a pattern-mixture model approach based on non-future dependent missing value restrictions (Kenward et al., 2003) will be performed to assess the robustness of the primary MMRM results to the possible violation of the missing-at-random assumption. The details of this sensitivity analysis are as follows:

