The pattern for the pattern-mixture model will be defined by the patient's last visit with an observed value. The observed CDRS-R total score at a visit is assumed to have a linear relationship with the patient's prior measurements. The missing values will be imputed under the assumption that the distribution of the missing observations differs from that of the observed only by a shift parameter value Δ . The dataset with missing values imputed will be analyzed using an ANCOVA model with treatment group and pooled study center as factors and baseline CDRS-R total score as a covariate for between-treatment group comparisons at Week 8. The imputation of missing values and the analysis will be performed multiple times and the inference of this sensitivity analysis will be based on the combined estimates using the standard multiple imputation technique. The range of values for the shift parameter Δ is selected as 0 to 6 based on experience with historical data.

More details of the proposed pattern-mixture model approach (e.g., the models for the pattern-specific identifiable densities and the unidentified conditional distributions, the shift parameter Δ , and the multiple imputation algorithm) are provided in Appendix I to this SAP.

To examine the consistency of the primary efficacy results across study centers, the treatment differences versus placebo treatment groups (mean \pm SE) in the change from baseline to Week 8 in CDRS-R total score will be graphed by pooled study center.

The comparison of fluoxetine vs. placebo will be performed to assess study assay sensitivity.

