Note that the two distributions only differ by a shift (Δ) parameter. When $\Delta = 0$, the missing value y_s in Pattern $s - 1$ is imputed based on the distribution of all observed data up to Visit s , as a result, leading to missing at random (MAR) missingness. When $\Delta \neq 0$, (8) will introduce a scenario of MNAR. The similar idea was also presented in the recent publication “The Prevention and Treatment of Missing Data in Clinical Trials” by the National Academies Press. The selection of the plausible values for the shift parameter (Δ) is discussed in Section 3 of this appendix.

Note that per recommendation in Wang and Daniels (2011), only the observed data within pattern is assumed to be multivariate normal. The observed data distribution can be expressed in terms of the marginal distribution of baseline measurement and the conditional distributions of postbaseline measurements given earlier measurements. Assuming that these distributions are normal, the linear regression of each observation on prior observations will yield least-squares estimates of model parameters that can be utilized for independent posterior draws of model parameters for observed data. Multiple imputation approach will be used to estimate the overall mean at the final time point.

2. Imputation Procedure

All the missing data will be imputed to create complete datasets, then statistical analysis can be performed using appropriate techniques such as ANCOVA. The imputation can accommodate MNAR missing data mechanisms, based on the theory discussed in the previous section.

The model parameters for each dropout pattern, i.e., the mean, variance and proportions of observations in each pattern, are drawn from their posterior distributions prior to the imputation of missing data for a single imputation.

The details of imputation within a pattern, say Pattern t , are as the following:

Step 1. Impute the first missing value y_{t+1} for each patient in Pattern t ($t = 1, \dots, T - 1$):

- a. Compute estimates of mixture probabilities $\lambda_{s-1,j}$ in (7) with $s = t+1$ given the posterior draw of proportions of observations in each pattern and the posterior draw of regression parameters for the observed data.
- b. Draw a random integer from $\{s, \dots, T\}$ to index a component distribution on the right hand side of (6), using mixture probabilities obtained in a). Draw y_{t+1}^* from the identified component normal distribution. Impute the missing y_{t+1} as

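### The missing-not-at-random check is confined to dosed patients with a post-baseline CDRS-R, so no efficacy estimate includes randomised patients with only a baseline score

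*SAP*

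**What the plan says.** SAP 6.3 defines the Safety Population as randomised patients "who received at least 1 dose of double-blind investigational product". SAP 6.4 then defines the ITT Population as "all patients in the Safety Population who had baseline and at least 1 postbaseline assessment" of the CDRS-R total score; Protocol 9.7.1.4 has the same rule. SAP 10.0 states: "The efficacy analyses will be based on the ITT Population".

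SAP 10.1 gives the primary MMRM two sensitivity analyses, LOCF and a pattern-mixture model. The pattern-mixture model is there "to assess the robustness of the primary MMRM results to the possible violation of the missing-at-random assumption". On its patterns: "The pattern for the pattern-mixture model will be defined by the patient's last visit with an observed value". Neither SAP 10.1 nor Appendix I names a different analysis set. The LOCF rule in SAP 10.0 does not carry the baseline value forward for a patient with no post-baseline score.

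Appendix I writes the observed-data distribution "in terms of the marginal distribution of baseline measurement and the conditional distributions of postbaseline measurements given earlier measurements". It imputes the first missing value for patterns t = 1 to T-1 and applies its shift equation (8) for s = 2 to T.

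**The concern.** A patient with a baseline score and nothing afterwards contributes nothing to an MMRM on change from baseline. That is harmless if such missingness is at random given arm, centre and baseline. The pattern-mixture analysis exists to relax exactly that assumption, yet the ITT rule removes these patients before it starts. Membership depends on taking a dose and on having a post-baseline assessment, and both happen after randomisation.

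If baseline is y_1 in Appendix I, Pattern 1 is the baseline-only group. The algorithm has an imputation step for it, and the ITT rule leaves it empty. The input is available: Protocol 9.3.1 makes a CDRS-R score at Screening and Baseline an entry condition.

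At stake is whether the sensitivity analysis supports the randomised comparison. If early loss differs between arms, or if imputation draws patients towards a common mean, the estimate that includes these patients differs from the one reported. Unequal loss is possible. Protocol 9.2 explains the titration by tolerability problems when treatment starts, and Protocol 9.5.2.1 draws attention to nausea and vomiting from the adult vilazodone programme.

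**Working it through.** **Inputs from the documents**

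- Design difference 4 points, correlation 0.7, dropout 17%, final SD 12.43, 188 per arm for vilazodone and placebo, 470 in total (SAP 14.0).
- Shift parameter Delta from 0 to 6 (SAP 10.1).
- Six post-baseline visits to Week 8 (Protocol 9.7.2: Visits 2 to 8, the first being baseline).

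**Assumptions**

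- 1% to 5% of each arm has no post-baseline CDRS-R.
- Dropout accrues evenly over the six visits.
- The 0.7 correlation is the same for all pairs of visits and includes baseline.
- The mixture probabilities in Appendix I are approximated by the pattern fractions.

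**1. The plan's own figure.** MMRM power with these settings and a two-sided 5% test is 84.5% at 188 per arm and SD 12.43 if dropout begins at the first post-baseline visit, and 85.0% if nobody is missing there. The SAP states 85%. For the initial 160 per arm and SD 11.1 the same method gives 86.7% and 87.2%. The settings are therefore a fair basis for what follows. The sample size is not in question here.

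**2. How many patients.** Even accrual gives h = 0.17/6 = 0.0283 before the first assessment: 0.0283 x 188 = 5.3 per arm and 0.0283 x 470 = 13.3 in total. The 1% to 5% range is 1.9 to 9.4 per arm.

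**3. How much of Delta reaches Week 8.** Take y_1 as baseline and a Pattern 1 patient. The full shift applies at y_2. Later values inherit part of it by regression, plus Delta again with probability delta. Per unit of Delta:

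- e_1 = 0 and e_2 = 1
- for s = 3 to 7: e_s = [0.7/(1 + 0.7(s-2))] x (e_1 + ... + e_(s-1)) + h/(1 - (s-2)h)
- e_3 = 0.4118 x 1 + 0.0292 = 0.441
- e_4, e_5, e_6 = 0.450, 0.458, 0.465
- e_7 (Week 8) = 0.1556 x 2.814 + 0.0330 = 0.471

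So K = 0.471. At Delta = 6 the Week 8 shift is 0.4707 x 6 = 2.82 points.

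**4. Effect on a difference of -4.00.** Let q_v and q_p be the excluded shares for vilazodone and placebo.

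- Imputation by arm: -4 + (q_v - q_p) x K x Delta.
- Imputation pooled over the two arms, with a common mean at the midpoint, 2 points from each arm: -4 + (q_v - q_p) x K x Delta + 2(q_v + q_p).

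| q_v / q_p | Delta | By arm | Pooled |
|---|---|---|---|
| 1% / 1% | any | -4.00 | -3.96 |
| 5% / 5% | any | -4.00 | -3.80 |
| 3% / 1% | 6 | -3.94 | -3.86 |
| 5% / 2% | 6 | -3.915 | -3.775 |
| 5% / 1% | 6 | -3.89 | -3.77 |

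The 5% / 2% row by arm moves 0.03 x 2.82 = 0.085 points. The largest pooled value in the range is the 5% / 1% row: 0.04 x 2.82 + 2 x 0.06 = 0.113 + 0.12 = 0.233 points.

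**5. Scale.** With no dropout, the standard error of the difference is 12.43 x sqrt(2/188) = 1.28. The two movements are 0.085/1.28 = 7% and 0.233/1.28 = 18% of one standard error, and 2% and 6% of the 4-point design difference.

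**The case against.** The other side has several good arguments.

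- **The loss would be seen.** SAP 7.0 tabulates the Randomized, Safety and ITT counts by arm, so the excluded number follows by subtraction. It also compares discontinuations by reason and lists the patients. A reader might infer that unequal early loss would go unnoticed; the documents do not support that. Only its effect on the estimate stays unseen.
- **Early stoppers are not all excluded.** Protocol 9.3.3 asks discontinuing randomised patients to attend an Early Termination visit with the Week 8 evaluations, and non-returners are written to. A patient who stops in the first days and attends can enter the ITT set. This stands, and it should keep the group small.
- **Informativeness is not shown.** A reader might infer that these are the patients whose missingness is most likely to be informative. The documents give no counts, reasons or split by arm for them, and the adult adverse events named in the protocol are not linked there to missing CDRS-R scores. The supportable statement is that their missingness may be informative.
- **Baseline as y_1 is an inference.** Appendix I speaks only of the measurement at Visit i. The factorisation that starts with baseline favours the reading used here. If y_1 were the first post-baseline visit, one more imputation step would be needed.
- **Keeping the MMRM set is coherent.** Holding the patients fixed isolates the missingness assumption. This is a fair reason to present the wider analysis as a supplementary run. It does not remove the gap, since no other efficacy analysis in the readable text covers these patients.

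**Conclusion.** The point holds, as a cheap improvement of modest size. The only planned analysis that departs from missing-at-random is restricted by post-randomisation events, and the plan gives no efficacy estimate that includes baseline-only patients.

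Under the stated assumptions, including them moves the estimate by zero (equal loss, imputation by arm), by about 0.085 points (a 3-point imbalance at Delta = 6), or by at most about 0.23 of 4 points (imputation pooled over arms). The SAP does not say which form of imputation applies.

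A reader might infer a larger bias by assuming that these patients end up 20 points worse, so that a 3-point imbalance gives 0.03 x 20 = 0.60. The documents do not support that. Twenty points is more than three times the largest planned Delta, and the product assumes that the whole deficit persists to Week 8, whereas under Appendix I less than half of Delta does. Nor would widening the analysis set reveal such a bias, because the planned shift range limits what the analysis can show.

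**What to change.** In SAP 10.1 and Appendix I:

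1. Define y_1 as the baseline CDRS-R total score.
2. Run the pattern-mixture analysis, or a supplementary run of it, on all Randomized Population patients with a baseline CDRS-R, so that Pattern 1 is populated and imputed.
3. State whether the imputation models are fitted by treatment arm or pooled.

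Leave the primary MMRM, the testing sequence and the sample size as they are. The cost is SAP wording, a little more analysis work with a few more imputed patients, and a sensitivity estimate that may be slightly less favourable.
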